## 1.0 OBJECTIVES / SPECIFIC AIMS

The objective of this study is to establish the safety, feasibility, tolerability, and acceptability of high-dose accelerated intermittent theta burst (iTBS) repetitive transcranial magnetic stimulation (rTMS) to the left dorsolateral prefrontal cortex (dlPFC) in patients with amnestic Mild Cognitive Impairment (aMCI). We also seek to obtain preliminary efficacy data as well as feasibility / acceptability data of computerized cognitive training as an adjunct to iTBS rTMS. The long-term goal of this project is to obtain preliminary data to support future empirical studies of iTBS rTMS for aMCI, including future randomized controlled trials to devise the optimum rTMS therapeutic delivery (with variations in dosing parameters, cortical targeting, and MCI syndrome indications), with the ultimate goal of dementia prevention. *The scientific merit of this pilot study has been peer-reviewed and subsequently recommended for funding through the National Center of Neuromodulation for Rehabilitation (NC NM4R).*

**AIM 1: Establish the safety of an accelerated rTMS protocol for neurocognitive rehabilitation in aMCI.** We hypothesize that accelerated rTMS will be safe as indexed by 1) no clinically significant structural brain changes; 2) no decrements in neurocognitive function; 3) no significant adverse events.

**AIM 2: Establish the feasibility, tolerability, and acceptability of an accelerated rTMS protocol for neurocognitive rehabilitation in aMCI.** We hypothesize that 1) aMCI patients will consider the treatment acceptable and that 2) recruitment and retention will be feasible (> 80% retention).

**EXPLORATORY AIM: Establish the preliminary efficacy of an accelerated rTMS protocol for neurocognitive rehabilitation in aMCI.** We hypothesize that aMCI patients will demonstrate modest improvements on neurocognitive testing and self-reported affective symptoms and quality of life from pre- to post-treatment.

**EXPLORATORY AIM: Establish the feasibility, acceptability of computerized cognitive training as an adjunct to accelerated rTMS in MCI.** We hypothesize that aMCI patients will complete a range of exercises between sessions and at home (feasibility) and will rate the intervention as productive (acceptability).

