In this open-label, safety and feasibility trial, we will recruit 40 amnestic MCI (aMCI) patients (target completers N=30) through memory disorders and neuropsychology clinics, as overseen by PI and neuropsychologist [name]. We will recruit clinically well-defined participants who will meet stringent actuarial neuropsychological criteria for aMCI. **This study will employ identical procedures to an ongoing IRB-I approved NC NM4R pilot, *Neuromodulation and Plasticity in Cognitive Control Neurocircuitry in Chronic Stroke* (PI: [name]; Pro 83136).** Specifically, neuronavigation-based targeting of the left dorsolateral prefrontal node of the cognitive control network will be performed. This study will utilize accelerated rTMS using a MagVenture MagPro TMS System. All participants will receive treatment for eight, 3-min sessions of iTBS on each of three days within an eight-day span. Each session would be separated by 10 mins or more per participant comfort and convenience. To collect preliminary feasibility and acceptability data for a planned follow-up combinatorial intervention study, participants will complete computerized cognitive exercises in the intervening periods between same-day rTMS sessions. At pre- and post-treatment, participants will undergo brain MRI (FLAIR, diffusion, T2\*/gradient, volumetric scans, resting state) and computerized neurocognitive testing. As an open-label pilot study, there is no sham control group.

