A therapeutic course of rTMS typically consists of 30-40 minutes of high-frequency (i.e. 10 Hz) treatment on each weekday, for 4-6 weeks. This schedule can be burdensome and reduce adherence. To improve upon this conventional approach, Co-I [name] et al. pioneered accelerated rTMS, demonstrating that delivering 3 high-dose sessions per day (i.e. 10 Hz; 3,000 pulses for 30 mins; 18,000 pulses/day total) on three consecutive days was safe, feasible, and suggestive of rapid antidepressant effects. More recently, a number of groups have demonstrated the feasibility, acceptability, and effectiveness of this form of delivery in which sessions are repeated daily, typically spaced by at least 30 minutes, to reduce total days of treatment. Safety has also been assessed with both structural and metabolic imaging as well as neurocognitive testing, which has shown no adverse effects and modest gains in cognition. Furthermore, acceptability studies show that accelerated rTMS increases adherence and decreases interruptions to daily obligations while yielding faster response. Importantly, critical to the success of this project is the fact that the procedures proposed in this study have already been approved by the MUSC Institutional Review Board for an NM4R pilot grant (PI: [name]: Pro 83136). As such, all methods are already established and running, personnel trained, and, importantly, we will be able to compare the results in two prevalent and functionally impairing neurodegenerative disorders.

**Computerized Cognitive Training.** To collect preliminary feasibility/acceptability data for a planned follow-up combinatorial intervention study, participants will complete computerized cognitive exercises in the intervening periods between same-day rTMS sessions. Clinical trials using the online system Brain HQ (<https://www.brainhq.com/world-class-science/science-team>) have been shown to be associated with cognitive function in older adults. Each exercise takes approximately 3-10 minutes and adapts to the individual's progress. The exercises fall under one of six categories: processing speed, memory, attention, people skills, cognitive flexibility and spatial navigation. During breaks between treatments, participants will complete exercises for a total of 20 minutes of exercises per day and 60 minutes of exercises over the

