three days of treatment. Afterwards, participants will be asked to complete at least 20 minutes of these exercises per day at home during the 4 weeks following treatment completion.

**RATIONALE:** Because accumulating work suggests that the 10-60 minute window following excitatory rTMS is a window of particular neuroplasticity, the longer-term plan of this line of work is to utilize rTMS as an adjunct for multimodal interventions including computerized cognitive training and behavioral interventions to optimize neuroplasticity, cognitive remediation, and quality of life. Toward this goal, we will collect preliminary acceptability/feasibility data of computerized cognitive exercises, interleaved between rTMS sessions.

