## 6.0 NUMBER OF SUBJECTS

The target completion is 30 participants. To contend with attrition, we propose to enroll 40 participants.

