**Sessions 3-5: rTMS (2 – 3 hours).** A MagVenture MagPro TMS System will be utilized. All participants will receive open-label treatment for approximately eight, 3-minute sessions of intermittent theta burst rTMS on each of three days within an eight-day span. A single session=600 pulses at 120% rMT, iTBS triplets at 50 Hz for 2 s and repeated every 10 s for a total of 190 s to left dlPFC. Total pulses=14,400. To enable adherence and retention, the days do not need to be contiguous. Same day sessions will be separated by 10-15 minutes, but more accounting for participant comfort. After each day of treatment, participants will be asked to complete an rTMS acceptability questionnaire. During treatment breaks participants will complete Momentary Assessment of TMS and 10-15 minutes of Brain HQ exercises between each session and will also have the option of completing tasks at home on intervening days during the treatment schedule. At the end of the final treatment session, participants will be asked to rate the exercises based on difficulty and enjoyment.

**Session 6: In-person Post-treatment Neurocognitive/Neuropsychiatric Assessment (2 - 3 hours).** Within one week following treatment, participants will repeat the pre-treatment neuropsychiatric and neurocognitive assessment for assessment of pre/post treatment changes.

**Session 7: Post-treatment MRI Scans (1 - 2 hours).** Within one week following treatment, participants will repeat the pre-treatment MRI scans for assessment of pre/post treatment changes.

**Session 8: 1 – 3 weeks post-treatment completion.** During the intervening weeks after Sessions 6/7 and before Session 9, the participants will be asked to remotely complete surveys using REDCap. Participants will also be provided with a research account for BrainHQ and asked to engage in at least 20 minutes of brain exercises daily until Session 9.

**Session 9: 4 weeks post-treatment completion.** Participants will again be asked to complete surveys using REDCap. Participants will also be asked to complete the MoCA remotely, as well as acceptability/satisfaction questionnaires regarding the rTMS and BrainHQ interventions.

**Participant Compensation.** Participants will be compensated as follows:

Consent & Session 1:	\$40 for screening and pre-treatment assessments
Session 2:	\$50 for the pre-treatment MRI
Sessions 3 to 5:	\$120 for rTMS treatment (i.e. \$40/day)
Sessions 6 and 7:	\$100 for post-treatment assessments and MRI

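### All participants train on BrainHQ before the Session 6 battery, in an amount the protocol states inconsistently, yet the pre-to-post change is labelled as rTMS efficacy

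*Combined protocol and SAP*

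**What the plan says.** The trial has one arm. Section 2.0 states: "As an open-label pilot study, there is no sham control group". Section 6.0 sets the size: "The target completion is 30 participants", from 40 enrolled.

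The first exploratory aim in section 1.0 is to "Establish the preliminary efficacy of an accelerated rTMS protocol for neurocognitive rehabilitation in aMCI". Its hypothesis is a modest pre-to-post improvement in cognition, affective symptoms and quality of life. Section 4.0 repeats the aim under the same label.

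Training is given to everyone. Section 2.0 says "participants will complete computerized cognitive exercises in the intervening periods between same-day rTMS sessions". The documents describe the amount and timing as follows:

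- **In clinic, section 3.0:** "participants will complete exercises for a total of 20 minutes of exercises per day and 60 minutes of exercises over the" three treatment days.
- **In clinic, section 10.0 (Sessions 3-5):** 10 to 15 minutes of BrainHQ in each break between sessions, with eight sessions a day.
- **Optional at home, section 10.0 (Sessions 3-5):** participants "will also have the option of completing tasks at home on intervening days during the treatment schedule". No amount is given.
- **Daily at home, section 3.0:** "participants will be asked to complete at least 20 minutes of these exercises per day at home during the 4 weeks following treatment completion".
- **Daily at home, section 10.0 (Session 8):** "Participants will also be provided with a research account for BrainHQ and asked to engage in at least 20 minutes of brain exercises daily", ending at Session 9. This stands in the entry for the weeks after Sessions 6 and 7.
- **Payment, section 10.0:** $4.50 per completed 20-minute exercise session, capped at $126.

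Sessions 6 and 7 fall up to a week after the last stimulation day. Section 12.0 analyses cognition, affect and quality of life with repeated-measures mixed models and names no term for BrainHQ exposure. Its power paragraph concedes that results are weaker without a sham group, and says the data will inform the effect sizes and variability expected in later randomised trials.

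**The concern.** A second active component is given to every participant before the outcome is measured, and neither the design nor the analysis separates it from rTMS. The protocol itself expects training to matter: section 3.0 says BrainHQ has been linked to cognitive function in older adults, lists memory, attention and processing speed among its targets, and justifies interleaving by the plasticity expected shortly after stimulation.

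The stated caveat does not cover this. A reader told only that there was no sham will discount for expectancy and retest practice. That reader will not know that the estimate also contains a training programme. A later trial of rTMS without BrainHQ could then be sized on a combined effect.

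The inconsistent training amounts add a second problem. If staff can follow either section, the combined intervention itself is not well defined, and the amount received before the battery can depend on which section was followed and when the appointment fell.

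**Working it through.** **The plan's own figures first.**

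- Payment cap: $126 / $4.50 = 28 sessions, which is 4 weeks x 7 days. This matches the home period in section 3.0. If home training began only after a Session 6 held on day 7, 28 - 7 = 21 days would remain, and 21 x $4.50 = $94.50.
- In-clinic total in section 3.0: 20 min x 3 days = 60 min, as stated.

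**In-clinic training before Session 6.**

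- Section 3.0: 60 min.
- Section 10.0: eight sessions leave 7 gaps a day. 7 x 10 = 70 min to 7 x 15 = 105 min a day; over 3 days, 210 to 315 min.
- Difference: 210 - 60 = 150 min to 315 - 60 = 255 min.

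**Requested home training before Session 6.**

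- Section 3.0, starting at treatment completion, at the minimum of 20 min a day, with Session 6 on day *d* after the last stimulation day: 20 x *d*. Day 0 gives 0 min, day 3 gives 60 min, day 7 gives 140 min.
- Section 10.0, read as starting after Sessions 6 and 7: 0 min.

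**Total requested exposure before Session 6.**

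- Lowest: 60 + 0 = 60 min.
- Highest: 315 + 140 = 455 min.
- Ratio: 455 / 60 = 7.6. It is never zero.
- Optional home practice is excluded. The 8-day span leaves up to 8 - 3 = 5 non-treatment days. The documents give no amount; at an assumed 0 to 20 min a day this adds 0 to 100 min, for a top value of 555 min.

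**Requested home training by Session 9.** 28 x 20 = 560 min under section 3.0; 21 x 20 = 420 min under section 10.0 if Sessions 6 and 7 fall on day 7.

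**Illustration of the labelling problem (assumed values, not from the documents).** Suppose rTMS has no effect, and training plus retest practice produce a standardised pre-to-post change *d*. With 30 completers, two-sided 0.05 and a normal approximation, the chance of a significant change is Φ(*d*√30 - 1.96) + Φ(-*d*√30 - 1.96). For *d* = 0.2, 0.3 and 0.5 this is 0.20, 0.38 and 0.78. Practice contributes to *d*, so these figures are not due to BrainHQ alone.

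**The case against.** The strongest reply is that this is an exploratory, preliminary aim in a safety and feasibility pilot, that combining the two interventions is openly planned, and that a single open-label arm could not isolate rTMS anyway because practice and expectancy are also unseparated. All of that is true and limits the weight of the point. It does not explain why the result carries the name of one component only, or why the limitation omits the other.

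A second reply is that Session 6 is already the natural time point. The hypothesis is pre-to-post, and the NIH Toolbox and the 30-minute neuropsychological battery are given only at Sessions 1 and 6. That is fair: naming Session 6 in section 12.0 is a clarification. It is still useful, because PROMIS recurs at Sessions 8 and 9 and the MoCA at Session 9.

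A third reply is that the home-start conflict is soft. In the Session 8 entry, the words placing events after Sessions 6 and 7 belong to the survey sentence; the BrainHQ sentence gives an end but no start. Home tasks are also allowed earlier, during the treatment schedule. The payment line covers computerised exercises without saying home only. So section 10.0 implies a later start rather than stating one, and the 28-session figure supports section 3.0 without proving it.

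Stronger readings that a reader might infer, and that the documents do not support:

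- *The timing conflict is what prevents attribution to rTMS.* It is not. In-clinic training precedes Session 6 on every reading, so settling the home start reduces the mixture but does not remove it.
- *The mixed models pool all visits as evidence for rTMS.* Section 12.0 does not say which visits or contrasts enter.
- *Training outweighs stimulation because it lasts many times longer.* Minutes of stimulation and minutes of software use are not comparable doses.
- *All later visits are mostly post-training.* By week 1 at most 140 of 560 requested minutes (25%) have passed.
- *Training is known to move these outcomes.* The protocol reports an association only.

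**Conclusion.** The point holds. The Session 6 change estimates rTMS together with BrainHQ, and results at Sessions 8 and 9 also follow requested daily home training. Calling the change efficacy of the rTMS protocol, and carrying it forward as an effect size with only the missing sham as a caveat, claims more than the design can give.

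The requested exposure before Session 6 runs from 60 to 455 min across the documents' own readings. The in-clinic discrepancy (150 to 255 min) is larger than the home-start one (0 to 140 min).

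This rests on three assumptions: seven breaks on each treatment day, Session 6 between day 0 and day 7, and home use at the requested minimum. Home use is asked for rather than enforced, so actual minutes may be lower or higher. The size of any training effect is unknown from the documents, so the bias cannot be quantified. The feasibility and acceptability of combined delivery remain legitimate aims, and nothing here argues for removing BrainHQ.

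**What to change.** 1. Reconcile sections 3.0 and 10.0, including the payment line, on the in-clinic training amount and on a home-training start that has the same relation to Sessions 6 and 7 for every participant. Which schedule to adopt is for the investigators; this review does not choose one.
2. In section 12.0, state Session 6 as the pre-to-post efficacy time point. Describe its result, and any effect size carried forward, as rTMS with BrainHQ. Describe results from Sessions 8 and 9 as the combined programme including home training.
3. Add concurrent training to the limitation in the power paragraph, beside the missing sham.
4. Report each participant's BrainHQ minutes before Session 6 as a descriptive summary, using the usage data already planned in section 4.0. Do not drop those who trained at home first: that would select on behaviour after baseline and on appointment date, among about 30 completers.

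The cost is protocol wording and one small table, with no new participants, visits or arms. The downside is a narrower efficacy claim.

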## **4.0 STUDY ENDPOINTS**

### **AIM 1: Establish the safety of an accelerated rTMS protocol for neurocognitive rehabilitation in aMCI.**

Primary Outcomes: Clinically significant structural brain changes; Neurocognitive performance changes; Adverse events

Secondary Outcomes: Psychopathology symptom changes

### **AIM 2: Establish the feasibility, tolerability, and acceptability of an accelerated rTMS protocol for neurocognitive rehabilitation in aMCI.**

Primary Outcomes: Patient perception of treatment acceptability; Recruitment rates; Retention rates

**EXPLORATORY AIM: Establish the preliminary efficacy of an accelerated rTMS protocol for neurocognitive rehabilitation in aMCI.**

Primary Outcomes: Neurocognitive performance changes

Secondary Outcomes: Subjective psychopathology symptom/Quality of Life changes

**EXPLORATORY AIM: Establish the feasibility, acceptability of computerized cognitive training as an adjunct to accelerated rTMS in MCI.** We hypothesize that aMCI patients will complete a range of exercises between sessions and at home (feasibility) and will rate the intervention as productive (acceptability).

Primary Outcomes: Rate of usage

Secondary Outcomes: Game performance change; subjective acceptability

## 5.0 INCLUSION AND EXCLUSION CRITERIA/STUDY POPULATION

Participants will be recruited through outpatient memory disorders and neuropsychology clinics staffed by neurologists and neuropsychologists at MUSC/DVA. (No procedures will be performed at the DVA; only recruitment materials will be provided.) Clinic providers will be trained on study criteria and procedures and will be provided with recruitment materials. [name] will oversee recruitment and will ensure that participants meet the following eligibility criteria:

### Inclusion Criteria:

- i. Age 60-85
- ii. English as a first/primary language
- iii. Has been diagnosed with MCI by a healthcare provider within the past two years per NIA-AA criteria: (1) Concern regarding cognitive decline reported by patient, informant, or clinician, (2) Objective evidence of impairment for age in 1+ cognitive domains, typically memory, (3) Preserved independent function, (4) no dementia.
- iv. Has met actuarial neuropsychological criteria for aMCI: (1)  $\geq 2$  impaired scores (i.e.  $\leq 16^{\text{th}}$  %ile) within one cognitive domain, or (2)  $\geq 1$  impaired scores (i.e.  $\leq 16^{\text{th}}$  %ile) in  $\geq 3$  cognitive domains, using demographically-corrected normative data. (1) and (2) must include the Memory domain.
- v. The primary suspected etiology of aMCI must be neurodegenerative, with competing differential diagnoses (e.g. psychiatric disorder, movement disorder, reversible causes, substance use) ruled out as the primary etiology/ies following a clinical evaluation by a healthcare provider.
- vi. Ability to provide independent informed consent, consistent with the MCI diagnostic criterion of preserved independent function.

### Exclusion Criteria:

- i. Dementia diagnosis per DSM-5 or NIA-AA criteria.
- ii. Daily/weekly use of anticholinergics, neuroleptics, sedatives, or bupropion. Stimulant use may be allowed pending investigator review. Cholinesterase inhibitors, NMDA receptor

antagonists, and antidepressants are allowed if on a stable regimen of four weeks prior to enrollment.

- iii. History of significant or unstable condition/s that may impact cognition such as significant cardiac, cerebrovascular, or metabolic disease, severe mental illness (e.g. bipolar disorder, psychoses), alcohol or substance use disorder, developmental disorder, or other neurologic disease (e.g. severe brain injury, seizures).
- iv. MRI and TMS contraindications (e.g., implants, claustrophobia, conditions/treatments that lower seizure threshold, taking medications that have short half-lives, no quantifiable motor threshold, active substance use disorder, bipolar disorder).
- v. Is enrolled in a clinical trial and/or has received an investigational medication within the last 30 days.

## 6.0 NUMBER OF SUBJECTS

The target completion is 30 participants. To contend with attrition, we propose to enroll 40 participants.

## 7.0 SETTING

All procedures will take place in private assessment and rTMS treatment rooms at the MUSC Center for Biomedical Imaging at [name]. The MRI scanning will also occur at the Center for Biomedical Imaging at [name] on the MUSC campus. Certain procedures, such as consenting and questionnaire completion may be completed virtually through telehealth using an MUSC approved electronic platform (e.g. musc.doxo.me or REDCap).

## 8.0 RECRUITMENT METHODS

### *Recruitment*

Participants will primarily be recruited through outpatient memory disorders and neuropsychology clinics staffed by neurologists and neuropsychologists at MUSC/DVA. Clinic providers will be trained on study criteria and procedures and will be provided with recruitment materials. A study coordinator will be on-call to facilitate rapid recruitment should a potential participant indicate his/her interest to the recruiting provider. [name] will oversee recruitment and will ensure that participants meet eligibility criteria.

Participant recruitment will also include flyers, handouts, electronic and physical bulletin board postings, social media/message boards (i.e., Craigslist, MUSC Broadcast Research studies section of Yammer, Instagram, Facebook), web-based recruitment tools (e.g., ResearchMatch, Trial Match), newsletter/newspaper/media advertisements, and recruitment talks at local community events/organizations and surrounding community. All approvals will be obtained prior to displaying flyers at the VA, and approvals will be obtained in other community locations if/as needed.

This project will also use an Epic-based tool that allows investigators to query clinical data for recruitment. The study team will receive a recruitment report from the Biomedical Informatics group containing a list of patients who potentially meet eligibility criteria. Study staff will then perform a chart review on these patients to further assess inclusion/exclusion criteria. Patients who appear to meet eligibility criteria and have opted in to being contacted about research will be contacted by the study team via phone, postal mail, and/or email.

Participants who make contact based on recruitment efforts will be given a description of the study purpose, procedures, and potential risks and benefits of the study by phone. The potential participant will be invited to ask questions until they are satisfied and can make a decision to proceed or not with the eligibility phone screen. If the potential participant agrees to continue, a phone screen will be conducted to determine eligibility for the next phase of the study.

